The aim is of this study is to explore the effect of a pain intervention (ie, trigger point injection) vs. a sham injection on managing post-surgical pain and reducing the reliance on systemic opioid analgesics. Outcomes include the VAS on POD1 and week 2 and week 6 follow-up appointments. Opioid use will also be evaluated during these intervals.

9.4 Study Design:

Describe study design in one to two sentences (e.g., prospective, use of existing records/data /specimens, observational, cross-sectional, interventional, randomized, placebo-controlled, cohort, etc.). Specify the phase – Phase I, II, III, or IV – for FDA-regulated investigational drug research

Prospective, interventional study comparing trigger point injections vs. sham injections on VAS pain scale ratings and opioid use.

9.5 Target Population:

Describe the population to whom the study findings will be generalized

DoD beneficiaries aged 45 years and older who will be receiving a TKA, on either knee.

9.6 Benefit to the DoD:

State how this study will impact or be of benefit to the Department of Defense

The purpose of this study is to explore a unique pain management modality to reduce the use of opioids following a routine surgery in the military hospital setting. This will benefit the Department of Defense by improving post surgical pain, decreasing overall opioid use which in turn may lead to decrease rate of opioid use disorders, shorter inpatient stays and decrease adverse medication side effects.

10.0

Study Procedures, Data Management, and Privacy

10.1 Study Procedures:

Describe step-by-step how the study will be conducted from beginning to end

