Step 1: A HIPAA Waiver will be used to access MHS Genesis to obtain all joint surgeons' case lists for those patients scheduled for surgery, all those not scheduled for a TKA will be removed from the list. The principal investigator will review case lists to identify name, TKA procedure, date scheduled for TKA, and phone. Patients scheduled for a TKA will be contacted within two weeks of their surgery to discuss the study. Study inclusion and exclusion criteria will be reviewed with patients who are interested in participation to ensure they are eligible. Those who are eligible will be scheduled for an appointment with the principal investigator before TKA surgery, ideally at their pre-op visit (standard of care visit) but may occur on the day of their surgery, to review consent documents and answer any questions. In order to ensure patient understanding, a copy of the consent documents will be emailed (if email address is provided) to the patient prior to the appointment to allow him/her to review the consent in advance.

Step 2: Patients return for their appointment to review and sign the consent documents either at their pre-operative visit or day of surgery. Consents will be signed either during their pre-operative appointment in a clinic exam room or during the day of their surgery in the PACU. Consenting a patient in the PACU on the day of surgery is a last resort and all efforts will be made to complete consents during pre-operative clinic visit. During the consent phase the PI and/or AI will not be in military uniform and will not have their rank displayed. After consent documents are signed, participants are assigned to a study group. Due to academic time constraints (i.e. deadlines to complete and present the research), an alternating convenience sample approach will be taken for study group assignment. Each participant will be assigned a subject ID number based on their order of enrollment (e.g., the first participant enrolled will be assigned 1, second participant enrolled assigned 2, and so on). Every participant with an odd number will be placed in the trigger point injection group (experimental) and those assigned an even number will be placed in the sham injection group (control). Those in the trigger point injection group will have an E after the number and

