those in the sham injection group an S. The study participants will not know which study group they will be assigned to. An equal number of participants will be included in each group (ie, trigger point injection vs. sham injection).

Step 3a: (Trigger point injection group) The principal investigator will identify relevant structures to include the vastus medialis, vastus lateralis, medial, and lateral gastrocnemius muscle bellies by utilizing anatomical landmarks. Once those structures are identified, each area will be prepped in an aseptic fashion with alcohol swabs. Two injections will be made in each muscle belly. Each injection will include 0.5 mL of 1% lidocaine without epinephrine. A total of eight injections will be administered with a total of 4 mLs of 1% lidocaine without epinephrine using a 1 ½" 25-gauge needle. A separate needle and syringe will be utilized for each of the four muscle bellies. Careful consideration to avoid neurovascular structures will be taken by retracting the plunger to ensure needle placement is outside vascular structures with each injection. A blind will be placed between the patient and the needle in order for the patient not to witness the injection, which is the same protocol as the sham injection. The blind used will be a drape or other soft item held by a person not involved with the study to obscure the vision of the subject during the injection and allow the investigator to use both hands to safely conduct the injection and aspiration procedure. The local anesthetic will be massaged into the area to ensure the medication disperses thoroughly into the muscle belly. After the needle is removed, the area will be cleaned with alcohol swabs and a bandage will be applied. This will be completed on POD 0 (ie, the day of the TKA procedure). Within the informed consent the consenting verbiage will ensure that the participants will not be able to identify injection technique that will identify whether they are in the sham or experimental group.

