on the region that best represents their pain and writing the number (a whole number) on the form; scores range from 0 (no pain) to 100 (severe intolerable pain). The Opioid Use questionnaire will be used to document average opioid use following discharge. Both questionnaires will be completed by all participants at POD1, week 2 and week 6 visits. The VAS will be given to the participant with the intake form that is provided by the orthopedic technician, and the investigator will provide the Opioid Use questionnaire to the participant during the visit, and review the MAR Summary to obtain and calculate the total MME from POD0 to POD1 using MDCalc . Prior to ending the visit, the investigator will ask participants to bring in their opioids to be physically counted at their week 2 and week 6 visits.

Step 6: The investigator will provide a reminder phone call 1-2 days prior to the week 2 and week 6 appointments to ensure participants remember to bring in their medication.

Step 7: Participants return for the week 2 and week 6 visits. They are given VAS and Opioid Use questionnaires to complete, and opioid medication is counted. Once opioids have been accounted for, MME will be calculated.

10.2 Data Collection:

Describe all the data variables, information to be collected, the source of the data, and how the data will be operationally measured.

Injection type: Dichotomous variable. Trigger point or sham injection.

Visual analogue scale: Discrete variable. Will be scaled from 0 (no pain) to 100 (severe intolerable pain) and will be measured at POD1, week 2, and week 6. The VAS will be presented to the participant on paper.

Morphine milligram equivalent (MME): Discrete variable. Will be measured from POD 0 to POD1, then a total MME will be calculated from POD1 to week 2 and week 2 to week 6. This will be calculated utilizing the MME calculator on MDCalc.

Block: Categorical variable. Spinal, adductor or femoral nerve block determined by anesthesiology.

Age: Continuous variable. Age stated in years at time of surgery as stated in EHR.

Prior Pain Medications: Categorical variable. Obtained from EHR.

Discharge disposition: Dichotomous variable. Discharge to skilled nursing facility or home, discharge disposition will be reviewed in the discharge summary.

Active Duty, Dependent, Retiree: Categorical Variable.

Sex: Categorical (male, female). Obtained from EHR.

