11.0 Statistical/Data Analysis Plan

11.1 Data Analysis Plan and Statistical Considerations:

List the statistical methods to be used to address the primary and secondary objectives, specific aims, and/or research hypotheses. Explain how missing data and outliers will be handled in the analysis. The analysis plan should be consistent with the study objectives. Include any subgroup analyses (e.g., gender or age group). Specify statistical methods and variables for each analysis. Describe how confounding variables will be controlled in the data analysis.

Demographic (age at time of surgery, BMI, sex, active duty/dependent/retiree status), medical (ICD code, nicotine use, history of diabetes, prior pain medications), laterality of the TKA (left or right), discharge disposition, and anesthetic block type (spinal, adductor, or femoral nerve block) data will be summarized overall and as a function of injection group using descriptive statistics (eg, mean, standard deviation, median, minimum, maximum, frequency, percentages) and 95% confidence intervals to describe the sample. Appropriate inferential statistics (eg, independent samples t tests, chi square tests) will be performed to determine if there are statistically significant differences in any of these variables between the two injection groups. If so, multivariable techniques (eg, ANOVA or regression) including these potentially confounding variables in the analyses and/or stratification will be undertaken.

VAS pain scores and the dosage (MME) of opioids will be evaluated in patients as a function of injection type (ie, trigger point injection vs. sham injection) at each time point. Data will be assessed for normality and homogeneity of variance to determine whether parametric (eg, independent samples t tests, repeated measures ANOVAs) or nonparametric (eg, Wilcoxon Mann Whitney tests, Skillings-Mack tests) methods are appropriate.

In addition, the number of patients with a VAS>40 (indicating a “significant” level of pain) will be calculated and compared in each group and at each time point using the chi-square test (or the Fisher’s Exact test if assumption regarding minimum expected cell counts is not met) as well as McNemar’s tests.

The critical alpha level will be set at .05. Missing data will be handled using the “pairwise deletion” method; this method still includes patients with some missing data in the analyses when possible.

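### No pain score is taken before the injection, so starting pain can be neither compared between arms nor adjusted for; one extra VAS form before surgery would be a cheap improvement.

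*Combined protocol and SAP*

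**What the plan says.** Three places in the combined protocol and SAP give the same VAS schedule. The objectives (9.3) state: "Outcomes include the VAS on POD1 and week 2 and week 6 follow-up appointments". The procedures (10.1, Step 5) state: "Both questionnaires will be completed by all participants at POD1, week 2 and week 6 visits". The variable list (10.2) says the score "will be measured at POD1, week 2, and week 6".

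The injection comes before all of these. Of the active injection, 10.1 Step 3a says: "This will be completed on POD 0 (ie, the day of the TKA procedure)", and Step 3b gives the sham the same timing. The chart review on the day of surgery (Step 4) and the rest of the 10.2 list contain no pain score. The nearest item is prior pain medications, a categorical drug history from the health record.

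On allocation, 10.1 Step 2 says "an alternating convenience sample approach will be taken for study group assignment": odd enrolment numbers receive the trigger point injection and even numbers the sham. Sections 11.1 and 11.2 plan 10-15 per group, with up to 50 if time and resources allow.

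On comparability, 11.1 lists demographics, medical history, prior pain medications, laterality, discharge disposition and block type, then says: "Appropriate inferential statistics (eg, independent samples t tests, chi square tests) will be performed to determine if there are statistically significant differences". Variables that differ significantly may then enter a multivariable or stratified analysis. Starting pain is not on the list.

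**The concern.** In a trial whose primary outcome is pain, pain before treatment is the covariate most directly tied to that outcome. It matters more here for three reasons.

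- Alternation makes the next arm predictable, so comparability does not have the protection that concealed randomisation gives. The plan's own safeguard is to check baseline variables and adjust, and that check leaves out starting pain.
- The planned groups are small, so sizeable chance gaps are likely.
- The trial is powered for differences of 28 to 35 units, and 11.5 concedes that the cited dry-needling trial saw less than 28 at one month. Any precision available at low cost is worth having.

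At stake are how far a reader can trust the arm difference and some statistical efficiency. A pre-injection score that is not recorded cannot be recovered later.

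**Working it through.** **Inputs from the documents (11.5, 11.1, 11.2).** Two-sided alpha 0.05, power 0.80, SD 25; 15 per group for 28 units (effect size given as 1.1; 28/25 = 1.12); 10 per group for 35 units (35/25 = 1.4); ceiling 50 per group.

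**Assumptions, not in the documents.** The baseline VAS also has SD 25. The baseline-to-follow-up correlation, rho, is unknown and is varied from 0.2 to 0.7.

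**1. The plan's own figures.** Wilcoxon power was taken from the noncentral t distribution with n multiplied by the asymptotic relative efficiency 3/pi = 0.955. Power is 0.81 at 15 per group and effect size 1.1 (0.82 at 1.12), and 0.82 at 10 per group and effect size 1.4. The stated sample sizes reproduce.

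**2. Chance gap in starting pain.** SD of the difference in baseline means = 25 × sqrt(2/n). The probability of a gap above 10 units in either direction is from the normal distribution.

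| n per group | SD of gap | P(gap > 10 units) |
|---|---|---|
| 10 | 11.2 | 37% |
| 15 | 9.1 | 27% |
| 50 | 5.0 | 5% |

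**3. Carry-over into the result.** With equal SDs, a baseline gap g shifts the unadjusted follow-up difference by rho × g. For g = 10 the shift is 3 units at rho 0.3, 5 at 0.5 and 7 at 0.7.

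**4. Precision, like for like.** The comparison is the t test (2n − 2 degrees of freedom) against ANCOVA (2n − 3). ANCOVA residual variance = 25² × (1 − rho²), inflated by 1 + 1/(2n − 4) for estimating the slope. At n = 15 the inflation is 1 + 1/26 = 1.038, so the net variance factor is 0.96 × 1.038 = 0.997 at rho 0.2, 0.91 × 1.038 = 0.945 at 0.3 and 0.75 × 1.038 = 0.779 at 0.5.

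| | Detectable difference, n = 15 | Power for 28 units, n = 15 | Detectable difference, n = 10 |
|---|---|---|---|
| No baseline (t test) | 26.5 | 0.84 | 33.1 |
| ANCOVA, rho 0.2 | 26.5 | 0.84 | 33.6 |
| ANCOVA, rho 0.3 | 25.8 | 0.86 | 32.7 |
| ANCOVA, rho 0.5 | 23.4 | 0.92 | 29.7 |
| ANCOVA, rho 0.6 | 21.6 | 0.95 | 27.4 |

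At rho 0.2 there is no gain at 15 per group and a slight loss at 10, where the slope inflation is 1 + 1/16 = 1.0625 and the net variance factor is 0.96 × 1.0625 = 1.02.

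**5. Would a significance-triggered rule be enough?** With SD 25 and 15 per group, a baseline gap reaches p < 0.05 only at 2.05 × 9.13 = 18.7 units. Adding the VAS to the 11.1 list while keeping that trigger would leave a 10-unit gap unadjusted.

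**The case against.** The strongest reply is that nothing is broken. The stated aim is a between-arm comparison of post-operative VAS, not change from baseline. That comparison is valid without a baseline score, and the sample size reproduces. Chance imbalance in starting pain is already part of the outcome SD of 25, so alpha and power allow for it. All of this stands.

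A reader might infer that any gap in starting pain passes in full into the arm difference. It does not: it carries over in proportion to rho, and only imbalance from selection is bias. A reader might also set the Wilcoxon's detectable difference (27.2 units) against a baseline-adjusted figure. That mixes two tests and overstates the gain at low correlation; the t test's 26.5 is the right comparator.

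The benefit does depend on an undocumented correlation, here between arthritic pain before surgery and surgical pain afterwards, and nothing in the documents shows that it reaches 0.5. The plan also allows 50 per group, where the chance gap shrinks to SD 5.0. That growth would not remove bias from predictable assignment.

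Partial cover exists. Prior pain medications and block type are collected and compared, and section 12.6 excludes chronic opioid users and patients with fibromyalgia. These are proxies or restrictions, not a pain score, and the collected variables are adjusted for only if the arms differ significantly. The POD1 score cannot serve as baseline because it follows the injection.

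**Conclusion.** The point holds as a cheap improvement. No pain score precedes the injection, and starting pain is outside the planned comparison and adjustment, so in a small alternating-assignment trial an imbalance can be neither seen nor corrected.

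Its size is moderate and conditional. With an assumed baseline SD of 25, a 10-unit gap would move the result by about 3-7 units at rho 0.3-0.7. The precision forgone at 15 per group runs from nothing at rho 0.2, through 0.7 units at 0.3 (26.5 − 25.8), to 4.9 units at 0.6 (26.5 − 21.6).

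The documents do not support the stronger reading that the primary comparison is invalid, that the sample size is wrong, or that a baseline score would make alternation safe. It would make imbalance in one measured variable visible and adjustable; predictable assignment remains a separate weakness.

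**What to change.** Have each participant complete the same paper VAS once, at the consent or pre-operative visit, before surgery and before assignment. The schedule already has such a contact (10.1 Step 1): "Those who are eligible will be scheduled for an appointment with the principal investigator before TKA surgery". Section 10.1 Step 3b expects the anaesthetic block still to be active at injection, so a score taken just then would be a poor measure of starting pain. Section 10.1 allows consent on the day of surgery while 13.1 rules it out; reconcile the two so that the timing of the form is clear.

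Add the baseline VAS to the 10.2 variable list. In 11.1, prespecify it as a covariate in the VAS comparison (ANCOVA or mixed model, or a rank-based ANCOVA if assumptions fail), whatever the baseline test shows.

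Cost: one extra form, about a minute per participant, and one degree of freedom. If the correlation is about 0.2 or lower there is little or no gain in precision, and a slight loss at 10 per group. The selection risk from alternating assignment is unchanged.

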There have been limited studies aimed at the treatment of myofascial pain syndrome in the acute setting of a TKA. Mayoral et al. (2013) conducted a randomized double-blinded, placebo-controlled clinical trial where patients who underwent a TKA had dry needling completed in the pre-operative and intra-operative setting. This study demonstrated an improvement in pain scores within the first month of surgery in the dry needling group compared to a sham group. This has been the only study to date to address direct intervention for myofascial pain syndrome around the operative time frame. Henry et al. (2012) conducted a prospective study in which patients on the waitlist for a TKA were treated with trigger point injections; patients reported an improvement in pain up until the TKA procedure could be completed. Although Henry et al. did not assess pain in the post-operative setting, this study nonetheless demonstrated that myofascial pain syndrome is a component of osteoarthritis.

Despite these favorable results there are no studies that look at trigger point injections in the post-surgical setting. The aim of this study is to perform trigger point injections with administration of a local anesthetic immediately following TKA to assess the effect on pain scores. The trigger point injection/experimental group will be compared to a sham injections/control group where a superficial injection will be made into the dermis and no anesthetic will be injected. Injections will include two injections to four muscle bellies: the vastus medialis, vastus lateralis, medial, and lateral gastrocnemius muscle belly. Injections will include 0.5 mL of lidocaine without epinephrine and will be outside of the operative area distal and proximal to the joint, the popliteal fossa and incision site. With each injection the plunger will be pulled back to ensure placement of the needle is outside vascular structures. To assess the primary outcome measures, patients will complete a Visual Analogue Scale (VAS) which ranges from 0 (no pain) to 100 (severe intolerable pain) on post operative day (POD) 1 and at follow-up visits during weeks 2 and 6. The secondary outcome will assess how much opioid medication (ie, MME) was used in the immediate post-operative period through the week 6 follow-up visit.

9.3

Objectives/Specific Aims/Research Questions:

Describe the purpose and objective(s) of the study, specific aims, and/or research questions /hypotheses

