BMI: Categorical variable. Obtained from EHR. Categories will be BMI of 24.9 or less, BMI 25-29.9, and BMI greater than or equal to 30.

Nicotine use: Dichotomous variable. Obtained from EHR. Current use at time of injury.

History of Diabetes: Dichotomous variable. Obtained from EHR.

ICD Code: Categorical Variable. Obtained from EHR.

Laterality: Categorical Variable. Left or Right TKA

Complications: Categorical Variable. Pulmonary embolism/deep vein thrombosis, surgical site infection, severe pain from the injections, other, and multiple for more than one complication.

10.3 At any point in the study, will you request, use, or access health information in any form, including verbal, hard copy and electronic?

Yes No

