The plan is to use 10-15 participants per group, although if time and resources permit, we will include more patients to increase the power of the study and

account for possible dropouts up to a maximum of 50 patients per group. Recruitment and enrollment will end once the target sample size has been achieved.

11.2 Sample Size:

The plan is to use 10-15 participants per group, although if time and resources permit, we will include more patients to increase the power of the study and account for possible dropouts up to a maximum of 50 patients per group (maximum of 100 patients total).

11.3 Total number of subjects requested (including records and specimens):

100

11.4 If you are recruiting by study arm, please identify the arms of the study and how many subjects will be enrolled in each arm

Experimental (ie, trigger point injection) group will include 10-15 patients (up to a maximum of 50 patients) and placebo (ie, sham injection) group will include 10-15 patients (up to a maximum of 50 patients). Recruitment and enrollment will end on 31 December 2025.

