Patients will be recruited through use of a HIPAA Waiver to access joint surgeon case lists. Patients scheduled for a TKA will be contacted by the principal investigator and informed of the study. Those who desire to participate will have study inclusion/exclusion criteria reviewed to determine eligibility. Those eligible will be scheduled a consent appointment. The investigator will offer to email (or provide by hard copy) consent document to review prior to the appointment. When patients return for consenting, they will be taken to a private room (clinic exam room or private room in the PACU) to conduct the consent procedures. Consent documents will be reviewed with patients and any questions asked will be answered. Patients who desire to enroll in the study will sign the consent documents. The investigator will sign the consent documents, then provide a copy to the patient. During the recruitment and consenting phase, the PI or AI will not be in military uniform or have their rank visible.

13.5 DoDI 3216.02 requires an ombudsman to be present during recruitment briefings when research involves greater than minimal risk and recruitment of Service members occurs in a group setting. If applicable, you may nominate an individual to serve as the ombudsman.

N/A
 Propose ombudsman

13.6 Withdrawal from Study Participation:

Explain the process for withdrawal and specify whether or not the subjects will be given the opportunity to withdraw their data or specimens in the event they wish to withdraw from the study

At any point in the study participants can self-withdrawal from the study if they have a poor response to the injections, are unable to tolerate all injections, not willing to complete questionnaires, intraoperative complications (pulmonary embolism, deep vein thrombosis, surgical site infection, multiple or other), not willing to bring in their medications or if they choose to no longer participate in the study. However, any data collected prior to withdrawal will still be analyzed.

14.0

Risks and Benefits

14.1

Risks of Harm:

Identify all research-related risks of harm to which the subject will be exposed for each research procedure or intervention as a result of participation in this study. Consider the risks of breach of confidentiality, psychological, legal, social, and economic risks as well as physical risks. Do not describe risks from standard care procedures; only describe risks from procedures done for research purposes

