Risk of breach of confidentiality. Other risks of harm include allergy to the medication used in the trigger point injection, pain, bleeding, injury to neurovascular structures, and infection. Being selected for the sham can potentially increase a patient's risk for pain.

14.2

Measures to Minimize Risks of Harm (Precautions, safeguards):

For each research procedure or intervention, describe all measures to minimize and/or eliminate risk of harms to subjects and study personnel

Risk is limited by coding the data, security limiting access of the data set to investigators, password protected files, and lock and key.

Injections will be performed by a trained provider under an aseptic technique by prepping the site with alcohol swabs. All injection sites will be marked utilizing landmarks to identify each muscle belly. The plunger will be retracted prior to injecting medication to ensure needle placement is not within a vascular structure. One needle and plunger will be used for each muscle belly to limit risk of infection. After completion of all injections the injection site will be cleaned with alcohol swabs and a bandage will be applied.

14.3

Confidentiality Protections (for research records, data and/or specimens):

Describe in detail the plan to maintain confidentiality of the research data, specimens, and records throughout the study and at its conclusion (e.g., destruction, long term storage, or banking). Explain the plan for securing the data (e.g., use of passwords, encryption, secure servers, firewalls, and other appropriate methods). If data will be shared electronically with other team members/collaborators outside the institution, describe the method of transmission and safeguards to maintain confidentiality. Explain whether this study may collect information that State or Federal law requires to be reported to other officials or ethically requires action, e.g., child or spouse abuse

Risk is limited by coding of the data set, password protection, locked cabinet /drawer, and security limiting access of the data set to investigators.

14.4

Potential Benefits:

Describe any real and potential benefits of the research to the subject and any potential benefits to a specific community or society

If the individuals in the research are considered experimental subjects (per 10 USC 980), and they cannot provide their own consent, the protocol must describe the intent to directly benefit all subjects

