Adverse events such as infection, damage to vascular structures that cause hematoma and excessive bleeding, injection of lidocaine into the blood stream are identified will be reported to the IRB. These adverse events will be monitored for during each visit through visually inspecting the injection sites and completing a neurovascular evaluation. The patient may also verbally inform the principal investigator of any of these potential adverse effects. The IRB will be notified by completing and submitting an eIRB Reportable Event Form (serious adverse event, unanticipated problem) or reporting at the time of continuing review (all others). The form will be routed to the DGMC C&T Board. The DGMC HRPP staff regularly monitor C&T Board notifications; they will notify the institution's HRPO of the reportable event by email, telephone, or in-person until it has been received and acknowledged. If any adverse event takes place the design of this study will be examined and determine if research protocol needs to be revised.

17.0**Equipment/non-FDA Regulated Devices**

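### The single Complications code in 10.2 gives only lower bounds for by-type counts and leaves three or four of the five named injection risks without their own level, so these harms cannot be compared by group from it

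*Combined protocol and SAP*

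**What the plan says.** Section 10.2 (Data Collection) has one harm variable: "Complications: Categorical Variable. Pulmonary embolism/deep vein thrombosis, surgical site infection, severe pain from the injections, other, and multiple for more than one complication". It is a single field with five levels, the last reserved for participants with more than one event.

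Section 14.1 (Risks of Harm) lists the physical risks of the study injection as "allergy to the medication used in the trigger point injection, pain, bleeding, injury to neurovascular structures, and infection". Section 9.2 places the injections "outside of the operative area distal and proximal to the joint, the popliteal fossa and incision site".

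Section 16.1 (Reportable Events) gives a separate route. It names "Adverse events such as infection, damage to vascular structures that cause hematoma and excessive bleeding, injection of lidocaine into the blood stream" for reporting to the IRB, and adds: "These adverse events will be monitored for during each visit through visually inspecting the injection sites and completing a neurovascular evaluation".

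Three other places bear on the point. Section 10.1, Step 4, takes complications from the medical record on POD0, and Steps 5 to 7 (POD1, week 2, week 6) name no further collection of them. Section 11.1 does not list complications among the variables to be summarized or compared. Section 13.6 uses a similar list when it describes withdrawal, "intraoperative complications (pulmonary embolism, deep vein thrombosis, surgical site infection, multiple or other", again with no level for bleeding, allergy or neurovascular injury.

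**The concern.** The coding loses information in two ways.

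First, the *multiple* level takes a participant out of every specific count. Those removed are the participants with the most harm.

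Second, apart from severe injection pain, the named levels describe complications of the knee replacement. The harms that belong to the study procedure mostly share *other* with unrelated surgical events. Under 10.1, Steps 3a and 3b, the active group receives eight intramuscular lidocaine injections, while the sham group has a superficial needle insertion with nothing injected. Bleeding, neurovascular injury and drug reaction are therefore harms on which the groups could plausibly differ, and this variable cannot separate them.

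At stake is the by-group description of injection harms. The pain score and opioid results are not affected.

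**Working it through.** The documents give no complication rate or count, so there is no figure of the plan's to reproduce. The check has three parts.

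**1. Risks in 14.1 set against levels in 10.2**

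| Risk in 14.1 | Level in 10.2 |
|---|---|
| Pain | Own level, but only when severe |
| Allergy | None named; goes to *other* |
| Bleeding | None named; goes to *other* |
| Neurovascular injury | None named; goes to *other* |
| Infection | Surgical site infection only; 9.2 puts the injections away from the incision |

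- Surgical site infection read literally: 5 − 1 = 4 of 5 risks have no level of their own.
- Surgical site infection taken to include injection sites: 5 − 2 = 3 of 5.
- Risks that cannot be coded at all: 0 of 5, because *other* accepts any event.

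**2. What can be recovered from the field**

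Let c be the number of participants at a level.

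- Named event type: the true number lies between c(type) and c(type) + c(multiple).
- Type with no named level: it lies between 0 and c(other) + c(multiple).
- Any complication: the sum over all five levels, which is exact.

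Example with assumed counts, 15 in a group: two participants have a DVT, and one of them also has a surgical site infection.

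| | True | Shown by the field |
|---|---|---|
| PE/DVT | 2/15 = 13.3% | 1/15 = 6.7% |
| Surgical site infection | 1/15 = 6.7% | 0/15 |
| *Multiple* | – | 1/15 |
| Any complication | 2/15 | 2/15 |

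**3. How large the loss to *multiple* could be**

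Assume k = 5 independent event types, each with risk p per participant. A participant with a given event is hidden if any of the other k − 1 also occurs:

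hidden share = 1 − (1 − p)^(k − 1)

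- p = 0.02: 1 − 0.98^4 = 7.8%
- p = 0.05: 1 − 0.95^4 = 18.5%
- p = 0.10: 1 − 0.90^4 = 34.4%

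Expected events of one type per group are n × p in truth and n × p × (1 − p)^4 as shown:

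| p | n = 15: true / shown | n = 50: true / shown |
|---|---|---|
| 0.02 | 0.30 / 0.28 | 1.00 / 0.92 |
| 0.05 | 0.75 / 0.61 | 2.50 / 2.04 |
| 0.10 | 1.50 / 0.98 | 5.00 / 3.28 |

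The group sizes come from 11.1 and 11.2: "The plan is to use 10-15 participants per group", with a maximum of 50 per group. The risks, the number of types and independence are assumptions. If complications cluster in the same participants, the hidden share is larger.

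**The case against.** The strongest reply is that little is lost in practice. A by-type count is understated only when one participant has two or more complications. At p = 0.05 the expected shortfall is 0.75 − 0.61 = 0.14 of an event per type at 15 per group, and 2.50 − 2.04 = 0.46 at 50 per group. Section 16.1 provides a second record, and with 20 to 30 participants those reports could be listed by hand, by type and group. Section 9.3 states no safety objective and 11.1 plans no analysis of complications, so no planned result changes.

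Much of this stands. A reader might infer that the event counts will be wrong. The documents do not support that: the understatement is conditional on co-occurring events, and the any-complication count is right in all cases. A reader might also infer that the injection harms have no category. They do, since *other* takes them; what they lack is a named level. And a flat four of five depends on reading surgical site infection as excluding injection sites, a term that 10.2 does not define.

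Two things remain. Pooling in *other* does not need co-occurrence: a single bleed or neurovascular injury is already indistinguishable from any other unlisted event. And 16.1 describes reporting to the IRB, not a dataset field or a summary by group; nor does it name allergy. That 11.1 omits complications is a further gap and does not make the coding adequate.

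**Conclusion.** The point holds as a defect of coding. As defined, the field gives the correct number of participants with any complication, lower bounds for each named event, and no separate count for allergy, bleeding or neurovascular injury, nor for injection-site infection on the literal reading (3 or 4 of the 5 risks in 14.1). These harms cannot be compared by group from this variable.

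This conclusion rests on the text alone. The size of the loss to *multiple* does not: 7.8% to 34.4% of a given event type, for assumed risks of 2% to 10%, five types and independence. In expected events this is small at the planned group size. The change is still worth making, because it costs very little and detail merged at collection may not be recoverable later.

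**What to change.** - **10.2 and the data form:** replace the variable with one yes/no item per event type, more than one allowed per participant. Keep the events already named, and add injection-site infection, bleeding or hematoma, neurovascular injury, and lidocaine reaction (allergic or intravascular). Keep *other* with a text field. Drop *multiple* and derive any complication from the items.
- **10.1, Steps 5 to 7:** complete the items at POD1, week 2 and week 6, using the injection-site and neurovascular checks already planned in 16.1. Without this, better items filled only from the POD0 record would still miss later events.
- **11.1:** add a descriptive summary by group, with the number and percentage of participants for each item and for any complication. No test is needed at this sample size.

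The cost is a slightly longer form and short edits to these sections. No new examination is needed, and clinical management does not change.
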